1. SUMMARY

Study description: This is a CORE protocol for an adaptive multiregional international global randomized, placebo-controlled trial to evaluate the safety and efficacy of drugs for the treatment of human monkeypox (Phase 3). Each site interested in participating can enroll patients in this international trial and implement the core protocol. This will require commitment to assess the main objectives as defined by the core protocol; enrolling homogenous population (common inclusion criteria); and evaluating the same interventions with the same primary and secondary endpoints. This adaptive design will allow future flexibility in testing several treatments.

Add-on studies Particular countries, or groups of centres may want to collaborate in assessing additional endpoints or to include further measurements or observations and include questions that are locally relevant (add-on trials).

Simplicity of procedures: Within each country or region, the national or regional Principal Investigators invites selected centres and helps them get ethical and regulatory approval and study drugs, then patient recruitment can begin. To facilitate collaboration, patient enrolment and randomisation are simplified, and core variables are collected using standardized definitions and will be sent in real time to a centralized data base (potentially across countries via a cloud-based GCP-compliant platform). All trial procedures are greatly simplified, and minimal paperwork is required. Once consent has been obtained, electronic entry of anonymised details of a few key characteristics of each patient takes only a few minutes. At the end of patient entry, a random treatment allocation is generated using a national (or by a global randomization center).

Quality requirements: centers sending these data should meet quality requirements (to be defined) that make them eligible to be part of the global analysis.

Eligibility: Adults and children (6 years and older) with laboratory-confirmed (PCR) monkeypox illness of any duration (provided that the patient has at least one active, not yet scabbed, lesion), and, who have no contra-indication to potentially study drug.

Consent: Once the information has been explained to patients, obtaining consent takes only a few minutes. An electronic image of the signature page is kept (or, if national regulations forbid this, a note to file), and the printed information and original consent stays with the patient or legal representative.

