
Data collected electronically immediately before randomisation. These include:

- Country, geographic region of residence, hospital and randomizing doctor
- Confirmation that informed consent was obtained from the patient (or a surrogate/representative)
- Age, sex and (yes/no): HIV, TB, malaria, hypertension, diabetes mellitus, asthma, hepatitis, hyperlipidemia, cancer, heart failure, renal disease, liver disease, chronic obstructive pulmonary disease (COPD), COVID-19, neoplasm, obstructive sleep apnea, obesity, immunosuppressive disorder other than HIV, sickle cell anemia, concurrent bacterial infections such as urinary tract, ear nose and/or throat, pulmonary, central nervous system, skin or gastrointestinal infection, bacteremia/sepsis or other.
- Date of onset of symptoms, date of hospitalization, and (yes/no) current/planned use of a few drugs
- Monkeypox lesions status (yes/no): at least one active, not yet scabbed, monkeypox lesion, other.
- Current symptoms (yes/no): nausea, vomiting, abdominal pain, anorexia, cough, lymphadenopathy, dysphagia, fever, headache, ocular lesions, and buccal ulcers.

- Smallpox vaccination status (yes/no) or presence of vaccination scar (yes/no).
- Risk factors for monkeypox infection (yes/no): recent contact with known monkey pox case, type of contact, residing or visiting an area with an active monkey pox outbreak, animal handling.

Trial entry; randomization: A participant will be considered enrolled beginning from when the informed consent form is signed and randomization to an assigned treatment has occurred. Once enrolled, study drug administration will begin according to study group assignment. Participants will be randomized to one of the experimental treatments (k in number) for which they are eligible (no specific exclusion criteria) or to one of the placebos that correspond (in appearance, dosing interval, and route of administration) to each of those treatments. The randomization ratio will ensure that participants have the same chance of receiving a placebo as they have of receiving each individual treatment for which they are eligible. All participants will also receive local SOC that is standardized at each site according to local/site guidance.

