Pregnant women and special populations will be enrolled in this study if the national principal investigator, the national regulatory authorities, and the ethics committee agree that the benefits of receiving the experimental treatment outweigh its risks, and specifically if they consent to participate after the information on risk and benefits is provided.

Study sites: Study sites will be in geographic locations where cases of monkeypox were reported. Sites will be opened one after another to ensure correct workflow of activities within a site and synchronization of activities between sites later on.

Study intervention: Details regarding dose administration for each evaluated treatment will be added here

Study Duration: The day when the subject is randomized to their assigned treatment arm is denoted as Study Day 1. Screening procedures will occur in the 24 hours prior to randomization (Study Day -1 to 1). Note that there is no Study Day 0. Study Day -1 is the 24-hour day prior to the day of randomization. The first day after randomization is Study Day 2. Subsequent days will be numbered chronologically through Day 58 of study.

Statistical considerations

Primary endpoint analysis: A stratified log-rank test will be used to compare arms with respect to time to lesion resolution², where stratification is by days from onset of symptoms to randomization (≤ 7 days vs > 7 days) and by baseline severity³. Participants with any lesions not scabbed or desquamated at 28 days after randomization will be censored for statistical analysis of this endpoint. Though deaths are expected to be relatively rare, deaths will also be censored at 28 days post-randomization.

Number of participants: The precise rates of clinical and microbiological resolution are uncertain for monkeypox in general, and for the current epidemiological context. The larger the numbers entered the more accurate the results will be. Realistic, appropriate sample sizes may not be estimated at the start of the trial; the numbers that can be entered will depend on the evolution of the outbreak.

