- Adults and children (6 years and older) with laboratory-confirmed (PCR) monkeypox illness of any duration (provided that the patient has at least one active, not yet scabbed, lesion and, who have no contra-indication to potentially study drug.
- Men and non-pregnant women of reproductive potential must agree to use effective means of contraception when engaging in sexual activities that can result in pregnancy, from the time of enrolment through the end of study participation. Acceptable methods of contraception include the following: hormonal contraception, male or female condom, diaphragm or cervical cap with a spermicide and intrauterine device.

Exclusion criteria

Exclusion criteria

- Current or planned use of another investigational drug at any point during study participation.
- Patients who, in the judgement of the investigator, will be at significantly increased risk as a result of participation in the study.
- Specific exclusion criteria for each evaluated drug will be considered.

Pregnant women and special populations will be enrolled in this study if the national principal investigator, the national regulatory authorities, and the ethics committee agree that the benefits of receiving the experimental treatment outweigh its risks, and specifically if they consent to participate after the information on risk and benefits is provided.

8. Study intervention

The details regarding the study treatments will be included in Appendix 1.

Dosing and administration

The details regarding dosing and administration be included in Appendix 1..

Dose modifications

No dosage adjustment is required for patients with mild, moderate, or severe renal or hepatic impairments at baseline.

Drug administration

Details regarding dose administration will be included in Appendix 1.

Preparation/handling/storage/accountability

Acquisition: Study treatment and placebo will be shipped to the study site where administration will take place, in compliance with all applicable transport guidelines.

Accountability: The study pharmacist will be responsible for maintaining an accurate record of the study arm codes, inventory, and an accountability record of study agent supplies.

Formulation, Appearance, Packaging, and Labelling:

Details regarding the study treatment will be included in Appendix 1

Product Storage and Stability:

Details regarding the study treatment will be included in Appendix 1

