Preparation: Details regarding the study treatment will be included in Appendix 1

9. Measures to minimize bias

Randomization

Once eligibility has been confirmed, subjects will be eligible for randomization. Randomization will be performed onsite.

Participants will be randomized to one of the experimental treatments (k in number) for which they are eligible (no specific exclusion criteria) or to one of the placebos that correspond (in appearance, dosing interval, and route of administration) to each of those treatments.

A randomization SOP will be developed prior to study start to provide details on the randomization process and procedures for maintaining the integrity of the randomization. The treatment allocation table and the program used to generate the treatment allocation table will be maintained by the data coordinating center on secure servers. The allocation table will not be revealed to anyone outside the unblinded team responsible for creating the table.

Screen Failures

Screen failures are defined as participants who consent to participate in the clinical trial but are not subsequently assigned to the study intervention or entered in the study. A minimal set of screen failure information is required to ensure transparent reporting of screen failure participants, to meet the Consolidated Standards of Reporting Trials (CONSORT) publishing requirements and to respond to queries from regulatory authorities. Minimal information includes demography, screen failure details, eligibility criteria, and any SAE. Individuals who do not meet the criteria for participation in this trial (screen failure) because of a modifiable factor may be rescreened. Rescreened participants should be assigned the same participant number as for the initial screening.

Blinding/Unblinding

Study team members, including the pharmacovigilance team, and participants will be blinded to treatment arm assignment throughout the duration of the study. To preserve blinding, after preparation, the drug or placebo will be placed outside the pharmacy for pick-up. The pharmacist will alert the responsible study team member that the treatment is ready to be picked up. The unblinded pharmacy staff is responsible for maintaining security of the study treatment assignments.

Scheduled unblinding: After all participants have completed the final study visit, the study will be unblinded and participants will be informed about their study treatment assignment by the study team.

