Appendix 1. Study intervention

(Information to be included)

Dosing and administration

Dose modifications

Drug administration

Preparation/handling/storage/accountability

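### Section 8 fixes a rule of no dose adjustment in renal or hepatic impairment for every product, in a core protocol that names no product

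*Protocol*

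**What the plan says.** Section 8 (Study intervention), under Dose modifications, consists of one sentence: "No dosage adjustment is required for patients with mild, moderate, or severe renal or hepatic impairments at baseline". It names no product, makes no exception and does not refer to Appendix 1.

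The surrounding text treats dosing as something to be supplied product by product:

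- Section 1 (Summary), Study intervention: "Details regarding dose administration for each evaluated treatment will be added here".
- Section 8, Dosing and administration: "The details regarding dosing and administration be included in Appendix 1".
- Section 8, Drug administration: "Details regarding dose administration will be included in Appendix 1".
- Section 8, Preparation: "Preparation: Details regarding the study treatment will be included in Appendix 1".
- Appendix 1 has its own Dose modifications heading with nothing beneath it. The whole appendix is marked "Information to be included".

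The Summary describes the platform as open-ended: "This adaptive design will allow future flexibility in testing several treatments". Sections 6, 9 and 12 refer to a number k of experimental treatments. No study drug is named in the body of the protocol; product names occur only in the reference list.

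The comorbidities recorded before randomisation (Sections 1 and 12) include "cancer, heart failure, renal disease, liver disease, chronic obstructive pulmonary disease (COPD"). Neither renal nor liver disease is a core exclusion in Section 7, which leaves drug-specific exclusions to be considered for each product.

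**The concern.** The need for dose adjustment in organ impairment follows from how a particular product is cleared and tolerated. The sponsor cannot know it for a treatment not yet chosen. Section 8 nevertheless answers the question for all treatments at once, up to severe impairment, and in definite terms. This is not detail left for later: it is a rule already stated, for products that are unknown.

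What is at stake is the safety of participants with renal or hepatic impairment. If a product that is usable in impairment at a lower dose joins the platform and the sentence is still there, a site that follows the core text would give the wrong dose. Sites in every participating country implement the same core protocol, so the sentence would travel with it.

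**Working it through.** No arithmetic applies, because the protocol gives no drug, no dose and no share of patients with impairment. The check sets the texts side by side.

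**1. Scope of the sentence.** Nothing in Section 8 ties it to one product. Sections 1, 6, 9 and 12 cover an unspecified number of treatments and foresee more. Read as written, it covers all of them.

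**2. Can such patients enter?** Section 7 sets the core criteria: PCR-confirmed disease with at least one active lesion, no contra-indication to the study drug, no other investigational drug, and no significantly increased risk in the investigator's judgement. Renal or hepatic impairment as such excludes no one. Both conditions are on the list recorded before randomisation, so such participants are possible.

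**3. What happens, by type of product.**

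| Property of the product | Effect of the sentence |
|---|---|
| No adjustment needed in any grade of impairment | The sentence is true; no one is affected. |
| Contra-indicated in impairment | The contra-indication criterion or a drug-specific exclusion keeps the patient out; the sentence has no effect. |
| Allowed in impairment, at a reduced dose | The patient can be randomised. Section 8 says no adjustment and the product's instructions say to reduce. Followed as written, the core text gives the wrong dose. |

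Only the third row causes harm, and only if the sentence is still in place when that product is added.

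**4. Do other provisions close the third row?** The eligibility provisions (Sections 7 and 12) decide who enters, not what dose is given. Section 10 lets the medical team depart from the allocated treatment where it judges this definitely appropriate. That permits an individual reduction, but it is case-by-case discretion and does not replace the stated rule.

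**5. Is there already a place for the right rule?** Yes. Appendix 1 has a Dose modifications heading that is still empty. The topic therefore has two homes: a generic one that is filled and a product-specific one that is blank.

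**The case against.** The strongest reply is that nothing is wrong today. Appendix 1 is unwritten, so nothing contradicts the sentence, and no one can be dosed until it is completed and national or regional approvals are obtained. Section 8 opens by placing treatment details in Appendix 1. Most readers would prefer a product-specific entry to a generic line, and filling in the appendix is a natural moment to reconcile the two. The eligibility safeguards and the freedom of the medical team are broad. All of this stands, and it is why the point is minor. It does not justify keeping a general statement that cannot be known to be true of products not yet selected.

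Several stronger readings are tempting but not supported:

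- *Participants are being, or will be, overdosed.* No product in the document is shown to need adjustment, and nothing links the sentence to a product in the reference list.
- *The sentence forbids adjustment.* It says that none is required, and Section 10 leaves room for individual deviation.
- *Dose modifications is the only part of Section 8 that is fixed in core text beside a matching appendix heading.* It is not. Acquisition and Accountability are also fixed there, so a count of headings that refer to Appendix 1 shows little.
- *The core text generally governs dosing over the appendix.* The duration of up to 14 days in Section 12 itself defers to another section through a broken cross-reference. In the text as read, it is not visible what the weight-based footnote c in Section 3 attaches to. Neither supports that inference.
- *A known share of participants is at risk.* The comorbidity list consists of yes/no items and shows possibility, not frequency.

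**Conclusion.** The point holds in a limited form. Section 8 states a product-specific property as a general rule in a core protocol that names no drug and is meant for several treatments, while patients with renal or liver disease are not excluded by the core criteria. The wording itself is certain; the consequence is conditional. It needs a product that is allowed in impairment at a reduced dose to be added while the sentence remains.

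The number of participants affected cannot be derived from the document. It is zero for any product that needs no adjustment. Severity is minor: this is a dosing-safety and drafting matter, and the primary endpoint, the analysis and the sample size are not affected.

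**What to change.** Replace the sentence under Dose modifications in Section 8 with: *Dose modifications, including any for renal or hepatic impairment, are specified for each product in Appendix 1.* Move the present sentence to the Appendix 1 entry of any product for which it is true. Where a product entry sets an adjustment, apply the same adjustment to its matched placebo so that the blind is kept.

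A general clause that Appendix 1 overrides core text should be left out, since the trial relies on common core text across sites. If a precedence rule is wanted, limit it to dose modifications.

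The cost is one sentence replaced and one moved. Visits, laboratory tests, endpoint, alpha and sample size do not change. The edit is best made before the first product is entered in Appendix 1.

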Data Monitoring Committee: A global Data Monitoring Committee (DMC) will monitor accumulating efficacy and safety data on an ongoing basis. The mission of the DMC will be to safeguard the interests of study participants and to enhance the integrity and credibility of the trial. The DMC will be asked to recommend stopping the study early for efficacy only when there is clear and substantial evidence of a treatment benefit. The PIs and Sponsors will make decisions about trial continuation based on recommendations received from the DMC.

² **Time to lesion resolution:** lesions of skin and mucosa are crusted, scabs have fallen off and a layer of skin has formed underneath

³ The definition of severity is being discussed.

2. Schema

[figure not shown]

Figure 1. Study Schema.

3. Schedule of Activities

Evaluation/Procedure	Screen	Baseline	Follow-Up		
Day +/- Window	-1 or 1	1	Daily if hospitalized, or every 3 to 5 days for outpatients ^d	28±7 ^a	58±7 ^b
OPERATIONAL AND CLINICAL ASSESSMENTS					
Informed consent	X				
Eligibility (inclusion/exclusion) assessment	X				
Demographics	X				
Medical history	X				
Randomization		X			
Vital Signs		X	X	X	X
Lesion Assessment ^e		X	X		
Record standard-of-care treatments		X	X		
Current symptoms		X	X	X	X
Assessment of AEs/SAEs		X	X	X	X
STUDY DRUG ADMINISTRATION					
Study drug administration		Treatment or placebo following schedule of administration of the drug			
RESEARCH LABORATORY EVALUATIONS					
Monkeypox PCR (blood) with CT	X ^g		Every other day if hospitalized, or every 3 to 5 days for outpatients if in virological sub-study		
Blood for storage		X	Day 14 for outpatients or earlier upon discharge for hospitalized patients (if feasible consider for outpatients)	X	X
Oropharyngeal and rectal lesions swab		X	For hospitalized patients: every other day until discharge; or every 3 to 5 days for outpatients if in virological sub-study		
Skin lesions swab		X	For hospitalized patients: every other day until discharge; or every 3 to 5 days for outpatients if in virological sub-study		

To be included in some sites if locally relevant and feasible

CLINICAL LABORATORY EVALUATIONS ^a					
Malaria rapid test	X				
Glucose (mg/dl)	X	X	Every other day until discharge	X	X
Hemoglobin (g/dL)	X	X	Every other day until discharge	X	X
Hematocrit (L/L)		X	Every other day until discharge	X	X
Creatinine (mg/dL)		X	Every other day until discharge	X	X
Potassium (mmol/L)		X	Every other day until discharge	X	X

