^e During lesion assessments any unresolved lesions in the target assessment region will be counted. While the participant still has unresolved lesions in the target region, assessment of whether there are unresolved lesions on other areas of the body will be optional but preferred. Once all lesions in the target region are resolved, a simplified full body lesion assessment will be done until all lesions are resolved.

^f All baseline assessments should be complete before starting study drug. Administration of the evaluated drug or placebo should be continued if the participant meets the criteria for discharge.

^g Although any positive monkeypox PCR from blood collected up to 48 hours prior to informed consent may be used to establish eligibility, a new specimen must be collected within 24 hours prior to randomization if the prior specimen is more than 24 hours old.

^h With the exception of screening collection of glucose and hemoglobin (both of which are required for determining eligibility), all labs at all time points, though highly desirable, may be waived if not feasible (e.g., due to blood draw volume concerns related to participant weight or due to site logistics), per investigator discretion. Any laboratory tests obtained within 24 hours from randomization for screening purposes do not need to be repeated on day 1.

4. Introduction

Study Rationale

WHO calls for the use of antivirals for the treatment of monkeypox cases within a framework of collaborative research and randomized clinical trial (RCT) protocols with standardized data collection tools for clinical and outcome data to rapidly increase evidence generation on efficacy and safety^{4,5}. This includes a scientific steering committee, common data management, and robust statistical analysis plan to satisfy regulatory requirements. Harmonised data collection for safety and clinical outcome (using WHO Global Clinical Platform for Monkeypox⁶) would represent a desirable minimum in the context of an outbreak such as current one.

A platform trial uses a shared infrastructure, in which various treatments are evaluated using the same 'CORE protocol' and tested against a shared control condition. Moreover, the speed of platform trials might help to accelerate the evaluation of drugs and generate evidence from different subgroups and different geographic locations.

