This randomization scheme is illustrated in Figure 2, where experimental treatments A, B and C, and their matched placebos, P_A, P_B and P_C, enter the trial at 3 different times. This design is efficient in allowing the assessment of each treatment to use a shared placebo arm with concurrent follow-up. Participants may be able to determine, based on specific characteristics, which treatment they might be receiving, yet will always be blinded to whether they are receiving the active treatment candidate or the corresponding placebo.

Study drug administration

Study drug administration will begin on Day 1 and continue for up to 14 days, as described in section 0.

SOC Received

All current SOC treatments will be recorded.

Current symptoms

Current symptoms and conditions will be recorded, including identification of any new or worsening (S)AEs as well as presence, of any bacterial complications such as urinary

tract, ear nose and/or throat, pulmonary, central nervous system, skin or gastrointestinal infection, bacteremia/sepsis or other.

Research laboratory evaluations (as part of add-on studies if feasible)

Blood will be collected via venipuncture for monkeypox PCR with CT, and blood will be stored for antibody titer measurements and other future research testing. Swabs will be collected from oropharyngeal lesions and open skin lesions for viral load assessments.

Clinical laboratory evaluations (as add on studies if feasible)

Laboratory testing, including urinalysis, will be performed as described in section 3. While every effort should be made to obtain these laboratories as indicated, note that the frequency and volume of blood draws is always subject to the clinical judgment of the site investigator as to safety and logistical considerations. Hence any inability to obtain the minimal laboratory assessments on a given day due to clinical or other extenuating circumstances will not constitute a protocol deviation.

Adverse reaction reporting

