Any suspected unexpected serious adverse reactions (SUSARs) that are life-threatening must be reported electronically within 24 hours of diagnosis, without waiting for death or discharge; as must any other potentially treatment-related serious adverse events (SAEs). Other adverse events do not need to be reported. A subset of countries or collaborators will also collect fuller information on adverse events. Where countries collect more extensive adverse reaction data, those datasets are not included in the CORE trial dataset.

In addition to reporting SAEs possibly related to the treatment and SUSARs, doctors will be asked, after patient discharge or death in hospital, what was the probable cause of death, and will be asked about drug use and respiratory support in hospital, including initiation of ventilation. Information on other non-fatal adverse outcomes is not in general required. It is, however, anticipated that some centres will choose to collect more detailed information on adverse events (eg, through linkage to medical databases) or on other aspects of outcome (eg, laboratory or radiological features), but this is not a requirement of the core protocol.

13. Statistical considerations

Design overview

This is a randomized, placebo-controlled, double-blind trial to test superiority of experimental treatments, as described above. **Figure 1** provides a study schema of the trial design. To date there have been no studies of monkeypox therapeutics in humans to inform the design of the present trial.

Populations for analyses

The primary analysis and secondary efficacy analyses will be based on a modified intention-to-treat population consisting of all randomized subjects who have a true positive monkeypox blood PCR result and grouped according to their true number of days since onset of symptoms for the purposes of stratification. Safety analyses including 28-day mortality, incidence of SAEs, incidence of AEs requiring drug discontinuation, and incidence of other AEs will be based a modified intent-to-treat population consisting of all subjects who received at least one dose of experimental treatment or placebo.

Statistical Analyses

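### The primary efficacy population requires a positive blood PCR, but the protocol contradicts itself on whether blood PCR is the eligibility test or an optional add-on

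*Protocol*

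**What the plan says.** Four places in the protocol bear on which PCR result counts.

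- **Section 13, Populations for analyses.** The primary and secondary efficacy analyses use a modified intention-to-treat population "consisting of all randomized subjects who have a true positive monkeypox blood PCR result". No sampling time is attached to that result, and nothing is said about a missing or negative blood PCR.
- **Section 7, Inclusion criteria (repeated twice in Section 1).** Eligible are "Adults and children (6 years and older) with laboratory-confirmed (PCR) monkeypox illness of any duration", given at least one active lesion. No specimen type is named.
- **Section 12, Research laboratory evaluations.** Under a heading that reads "Research laboratory evaluations (as part of add-on studies if feasible", the text says "Blood will be collected via venipuncture for monkeypox PCR with CT".
- **Section 3, Schedule of Activities.** The row "Monkeypox PCR (blood) with CT" is marked at Screen. Its footnote g says that "any positive monkeypox PCR from blood collected up to 48 hours prior to informed consent may be used to establish eligibility", and that "a new specimen must be collected within 24 hours prior to randomization if the prior specimen is more than 24 hours old". During follow-up, blood PCR is every other day for hospitalised patients; outpatients have it only if they are in the virological sub-study.

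A related inconsistency concerns mortality. Section 5.2 lists 28-day all-cause mortality as a secondary endpoint under clinical efficacy, and Section 13 tests secondary endpoints in order after the primary. Yet the paragraph on analysis populations names 28-day mortality among the safety analyses, which use everyone who received at least one dose.

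**The concern.** The analysis population is narrower than the enrolled population as the inclusion criterion defines it. The result that decides membership comes from a test that one section treats as optional and another as part of screening. A participant who satisfies every written eligibility criterion can be randomised, treated and followed, and then not appear in any efficacy analysis.

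Three things are at stake:

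- The primary result may describe blood-PCR-positive participants rather than the population enrolled.
- Lesion-resolution events are lost in proportion to the excluded share.
- With no sampling time stated, the text does not rule out that a blood result obtained after randomisation confers membership. Viral clearance is itself an outcome in Section 5.2, so a treatment could then influence who is analysed.

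**Working it through.** **Step 1. Set the passages side by side.** They allow two readings.

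- *Reading A (inclusion criterion plus Section 12).* Confirmation may come from any specimen and blood PCR is done where feasible. Someone confirmed on a lesion swab with blood negative or untested is eligible and randomised, but falls outside the set in Section 13.
- *Reading B (schedule plus footnote g).* Blood PCR is the eligibility test. Almost everyone randomised is then blood-positive, and the word true in Section 13 mainly removes false positives.

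Footnote g does not settle the matter. It permits a blood result for eligibility without excluding other specimens. It requires a new specimen when the earlier one is over 24 hours old, but does not require that specimen to be positive before randomisation. Even under Reading B, a participant can have a positive first and a negative second blood result, with no statement of which one counts.

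**Step 2. Reproduce the protocol's own figure.** Inputs from Section 13, Number of participants: rate ratio 1.4, power 90%, false positive rate 2.5%. Section 12 gives 1:1 allocation of each treatment against shared placebo. Schoenfeld's formula, with the 2.5% taken as one-sided (the same as two-sided 5%), gives

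events = 4 × (1.960 + 1.282)² / (ln 1.4)² = 4 × 10.507 / 0.1132 ≈ 371.3, rounded up to 372.

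This matches the stated 372, and the power at 372 events is 90.1%. The figure is not in error.

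**Step 3. Size of the loss.** The protocol gives no blood-PCR-positive share. Call it q and treat it as an assumption. Suppose 372 events occur among all randomised participants in a comparison and resolution rates do not differ by blood status. Then

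- events analysed = 372 × q
- power = Φ(√(372q) × ln(1.4)/2 − 1.96)
- events needed among all randomised to keep 372 in the analysis set = 372 / q

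| Assumed q | Events analysed | Power | Events needed among all randomised |
|---|---|---|---|
| 1.0 | 372 | 90.1% | 372 |
| 0.9 | 335 | 86.8% | 414 |
| 0.8 | 298 | 82.7% | 465 |
| 0.7 | 260 | 77.5% | 532 |
| 0.5 | 186 | 63.1% | 744 |

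If the 372 events are instead counted within the analysis set, power stays at 90% and the cost appears as enrolment, by a factor 1/q (1.1 at q = 0.9, 2.0 at q = 0.5).

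**Step 4. Bias between arms.** If only pre-randomisation blood decides membership, the restriction is a baseline subset. It costs power and generalisability but does not bias the comparison. If later results could confer membership, a participant positive at baseline would stay in whatever the drug does. Only those blood-negative or untested at baseline could enter through a later result. Outpatients outside the sub-study have no scheduled blood PCR during follow-up, so the opportunity to enter that way would also differ by setting.

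**The case against.** The strongest reply is that blood PCR is plainly the screening test. It is the only PCR marked at Screen, since the oropharyngeal/rectal and skin swab rows start at Baseline. Footnote g speaks of eligibility and makes a fresh specimen mandatory when the earlier one is old. The restriction to sub-study participants appears only in the follow-up cell for outpatients.

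Nor is the Section 12 heading strong evidence that the test is optional. The parallel heading there also calls clinical laboratory tests add-ons if feasible, yet footnote h says screening glucose and hemoglobin are required for determining eligibility. On this view few participants are lost.

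Much of this stands. A reader might infer from Sections 7 and 12 alone that the protocol certainly drops a sizeable group of eligible participants and is underpowered as a result. The documents do not support that. The exclusion follows from one of two conflicting readings, no blood-positive share is given, and 372 is an illustration with no sample size attached.

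A reader might also infer that treatment determines membership. That is not supported either. Section 13 pairs the PCR condition with the true number of days since onset, a baseline fact, so correction of baseline misclassification is a natural reading. The sampling window might also be left to the statistical analysis plan.

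What the reply does not remove is the contradiction. The inclusion criterion names no specimen, footnote g is permissive and requires no positive repeat, and Section 13 restricts the primary analysis to blood positives.

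**Conclusion.** The concern holds as an internal contradiction about the PCR that defines the primary population. Section 3 (footnote g), Section 7, Section 12 and Section 13 cannot all be followed without leaving some participants' membership undetermined. Because this decides who is in the primary analysis, it should be resolved before the trial is unblinded.

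The size of the effect cannot be derived from the protocol. It is small if blood PCR is the eligibility test. Otherwise it depends on the assumed share: a power loss of about 3 points at 0.9 and about 27 points at 0.5, if 372 events are counted among all randomised and resolution rates do not depend on blood status. Bias between arms arises only if post-randomisation results can confer membership, which the text neither states nor excludes.

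The placement of 28-day mortality is a separate inconsistency. The same endpoint is classed as secondary efficacy, which implies the blood-PCR set, and also as a safety analysis in the dosed set.

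**What to change.** Reconcile footnote g of Section 3, the inclusion criterion, the Section 12 heading and the population paragraph of Section 13:

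1. Define the efficacy population as all randomised participants, analysed as randomised, with PCR confirmation from any pre-randomisation specimen accepted for eligibility.
2. Exclude only false positives, judged on pre-randomisation specimens by assessors blind to arm.
3. Present blood-PCR-positive participants as a subgroup or sensitivity analysis.
4. If blood positivity is truly intended, write it into the inclusion criterion instead, make the pre-randomisation blood test part of the core protocol, and state which result counts when two are available.
5. Give 28-day mortality one stated population for the testing hierarchy, preferably the same efficacy population, and keep the dosed set for the safety summary.

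Items 1 to 3 and 5 change wording only and need no extra patients or tests. Item 4 would make the blood test obligatory at every site and could narrow enrolment.
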